3.0 Patient Eligibility

Inclusion Criteria:

- 1. Patients with Idiopathic Myelofibrosis or Myelofibrosis secondary to Polycythemia Vera or Essential Thrombocythemia.
- 2. Patients 18 to less than or equal to 70 years.
- 3. Patients wanting to pursue transplant.
- 4. Patients must have a Zubrod PS equal or less than 2.
- 5. Calculated creatinine clearance greater than 50ml/min. using the Cockcroft-Gault equation.
- 6. Ejection fraction equal or above 40%.
- 7. Serum direct bilirubin less than 1 mg/dl (unless due to Gilbert's syndrome or hemolysis).
- 8. SGPT equal or less than 4 x normal values.
- 9. Corrected DLCO equal or above 50% of expected.
- 10. Negative Beta HCG test in a woman with childbearing potential defined as not post-menopausal for 12 months or no previous surgical sterilization) and if fertile, males and females must agree to use contraceptives.

Exclusion Criteria:

- 1. Patients with low risk myelofibrosis (Appendix J:DIPSS plus criteria).
- 2. Uncontrolled life-threatening infections.
- 3. HIV positive.
- 4. Patients with active viral hepatitis.
- 5. Prior treatment with Pacritinib.
- 6. Prior stem cell transplant.
- 7. QTc greater than 450 ms.
- 8. CYP3A4 strong or moderate inhibitors/inducers in the past 7 days.

4.0 Treatment Plan

4.1 The investigational agent for this study is Pacritinib.

- 4.1.1 Patients will start Pacritinib 200 mg po bid.
- 4.1.2 Patients can proceed to transplant after 60 days of starting Pacritinib but not more than 180 days.
- 4.1.3 Pacritinib will be stopped 21 days prior to starting preparative regimen for SOC Allo TP.
- 4.1.4 If for whatever reason a patient cannot pursue or receive SOC Allo TP, they will be able to continue treatment with Pacritinib until there is evidence of disease progression.
- 4.1.5 A patient will still be able to proceed to SOC ALLO TP if for any reason they cannot complete 60 days of treatment prior to transplant.
- 4.1.6 If a patient vomits or misses a dose, will continue treatment with the next scheduled dose. Missed doses and reason for non-compliance will be recorded.
- 4.1.7 Every effort should be made to avoid CYP3A4 inducers or inhibitors (see Appendix H) while patients are on pacritinib. If concomitant therapy with CYPsA4 inhibitors or inducers is medically necessary and there are no available or suitable substitutes, this should be documented in the patient's medical record and extreme caution taken with their continued use during the study duration.
- 4.1.8 Patients will document compliance of taking medication on a patient diary.

4.2 Treatment Interruption:

Safety parameters including AEs, hematology, and serum chemistry will be monitored according to the protocol. Pacritinib treatment may be withheld for up to 4 weeks due to drug-related toxicities. A longer recovery period may be allowed based on the toxicity, but must be agreed upon between the investigator and medical monitor. After treatment interruption, patients may resume the pacritinib treatment at the same dose level or at a reduced dose level. No dose re-escalation is allowed.

4.3 Pacritinib Dose Management Guidelines for Pacritinib-Related Nonhematologic Toxicities:

- 4.3.1 A maximum of 2 dose reductions is allowed. The first dose reduction will be a 100 mg reduction from the original dose. The dose will be reduced to 200 mg Q AM and 100 mg Q PM
- 4.3.2 The second dose reduction will be another 100 mg reduction and the dose will be reduced to 100 mg BID.
- 4.3.3 Once the dose is reduced, no re-escalation is allowed.
- 4.3.4 Dose management for nonhematologic toxicities is summarized in Table 3.

Table 3 Treatment Toxicity and Dose Management: Pacritinib-Related Nonhematologic Toxicities		
CTCAE Toxicity Grade	Management/ Action	
1 or 2	No change.	
3	 Hold treatment. If the toxicity resolves to grade ≤ 1 or to the baseline grade within 7 days, treatment may be resumed at the same level or the next lower dose, at the discretion of the investigator after discussion with the sponsor. Toxicity that does not resolve to grade ≤ 1 or to the baseline grade within 7 days requires dose reduction to the next lower dose level. 	
4	 Hold treatment. If the toxicity resolves to grade ≤ 1 or to the baseline grade within 7 days, treatment may be resumed, but dose will be reduced by one dose level from the level at which the toxicity was observed. If grade 4 toxicity occurs at the lowest dose of 200 mg/day, the patient should be discontinued from the study. 	

4.3.6 The lowest dose of pacritinib used in the study will be 200 mg/day. If toxicity persists despite dose reduction to 200 mg/day, the patient should be discontinued from treatment.

4.4 Dose Management Guidelines for Hematologic Toxicities:

- 4.4.1 Myelosuppression is an expected event in patients with MF. However, myelosuppression with associated complications such as fever, infection, or bleeding or myelosuppression that worsens during treatment (based on local laboratory values) must be reported as an AE.
- 4.4.2 Patients with myelosuppression may receive supportive care including transient use of granulocyte colony stimulating factor for the treatment of febrile neutropenia and transfusion as clinically indicated.
- 4.4.3 Patients receiving pacritinib are not allowed to receive hematopoietic growth factors such as erythropoietin for the treatment of anemia.
- 4.4.4 Patients with clinically significant worsening of myelosuppression (as judged by the investigator and based on local laboratory values) for more than 7 days or myelosuppression associated with infection or bleeding should have pacritinib dosing interrupted. Pacritinib may be restarted at a reduced dose once the toxicity has resolved to grade ≤ 2 or to the baseline grade and the complications of myelosuppression such as infection or hemorrhage have resolved.

4.5 Allogeneic graft:

Peripheral blood (PB) or bone marrow (BM) progenitor cells may be used in this study peripheral blood will be preferred.

4.6 **Preparative Regimen**:

SOC transplant conditioning with Fludarabine and Busulfan AUC of 4000 microMol-min per day providing that pharmacokinetic can be done, otherwise Busulfan dose will be given as a fixed dose of 100 mg/m² daily for four days. A SOC treatment plan and informed consent will be used for this.

4.7 GVHD Prophylaxis and Supportive Care as per standard practice in patients receiving allogeneic transplant:

Recipients of matched related and unrelated donors will receive tacrolimus and Mini Methotrexate as per institutional standard.

Recipients of matched or one antigen mismatched unrelated donors will receive anti thymocyte globulin (ATG) tacrolimus and Mini Methotrexate as per institutional standard. Patients who do not have a suitable related or unrelated donor and who are going to undergo transplant from a haploidentical donor will come off study.

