5.0 Evaluation During Study

5.1 Disease Assessment Prior to Start of Pacritinib (baseline):

- a) Patient medical history and physical examination including measurement of liver and spleen size by physical examination or imaging (MRI or CT or ultrasound if possible) with addition of marrow-specific MRI sequences.
- b) CBC, differential and platelet count
- c) Bone marrow aspiration and biopsy
- d) Chemistry panel
- e) Serology for CMV, HBV, HCV and HIV
- f) B-HCG in women of childbearing potential
- g) 2 D echo, EKG
- i) Pulmonary function tests with DLCO
- j) Chest x-ray
- k) MF symptoms questionnaire (Appendix D.)
- I) Fact BMT questionnaire (Appendix E.)
- m) Blood for immunological profile if patient agrees to consent to optional study.

5.2 Follow up each month while on Pacritinib:

Patients will come to MDACC once each month to pick-up the next month's Pacritinib and have the following done. The monthly visits will continue as long as patient is taking Pacritinib.

- a) Medical history and physical examination
- b) CBC, differential and platelet count
- c) Chemistry panel
- d) EKG

Cycle 1 only: Day 14 (+/- 2 days) CBC, differential and platelet count and chemistry panel. These can be drawn locally and results sent to MDACC. The PI/treating physician must review outside lab results, determine clinical significance, sign and date the outside lab results.

Cycle 1 only: During week 2, study personnel will call patient about any new symptoms.

Patients treated on this protocol may require supportive care treatment (concomitant medications). These medications are considered standard of care and have no scientific contribution to the protocol; therefore no data will be captured on various medications needed or their side effects.

5.3 Within about 7 days after completion of Pacritinib (but before transplant):

- 1) Physical examination including measurement of liver and spleen size by physical examination or imaging (MRI or CT or ultrasound if possible).
- 2) EKG
- 3) Bone marrow aspiration and biopsy

5.4 Post-transplant Evaluations:

- 5.4.1 Post-transplant evaluations will follow our standard practice and are done to monitor engraftment and disease status.
- 5.4.2 Additional post-transplant follow-up specific to this study at approximately 1, 3, 6, and 12 months post-transplant:
 - 1) At around 3 months:
 - Measurement of liver and spleen size by physical examination or imaging (MRI or CT or ultrasound if possible).

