6.0 Statistical Considerations

General

This will be a single-arm, Phase II study of pacritinib, fludarabine, and busulfan as a preparative

regimen in allogeneic stem cell transplantation in patients with myelofibrosis. The primary endpoint is progression-free survival (PFS) in patients undergoing matched related or at least 7/8 matched unrelated donor transplant. We will enroll at least 21 evaluable patients, defined as patients who undergo transplant with a matched related or at least 7/8 matched unrelated donor. Patients who do not have a suitable related or unrelated donor will come off study and may receive a transplant from a haploidentical donor. For this reason and because some patients may decide not to undergo transplant after starting the drug, we may need to enroll up to 40 patients to ensure that 21 are evaluable for our primary endpoint.

Endpoints

6.1 Primary End Point (Progression-Free Survival):

Progression-free survival is defined as the time of stem-cell transplant to the time of death or disease progression.

6.2 Secondary End Points:

Neutrophil Engraftment is defined as a sustained ANC \geq 0.5 x 10 $^{\circ}$ /L for 3 consecutive days and evidence of donor chimerism by D+28 (the first chimerism study will be done 3-4 weeks post-transplant).

Platelet Engraftment is defined as a sustained first of three consecutive laboratory values of platelet $\geq 20x109/L$ with no platelet transfusions administered for 7 consecutive days.

Non-relapse mortality is defined as death without disease progression.

Liver response will be defined by the change in the size of the liver measured below the coastal margin in the mid-clavicular line by palpitation.

Spleen response will be defined by the change in the size of the spleen measured below the coastal margin in the mid-clavicular line by palpitation.

Quality of life will be measured by the QOL FACT BMT.

Symptom score will be measured by the MPD symptom score.

Immune recovery will be measured by various cell subsets and cytokine levels.

Primary Graft Failure is defined as failure to achieve an ANC \geq 0.5 x 10 $^{\circ}$ /L for 3 consecutive days by day 28, with <10% cellularity on bone marrow biopsy and no evidence of donor chimerism.

Secondary graft failure is defined as a sustained declined of ANC <0.5 x 10°/L for 3 consecutive days after initial documented engraftment with no evidence of disease progression.

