We will use descriptive statistical methods to tabulate safety parameters such as the rate of adverse events. Only patients who undergo transplant with a matched related or at least 7/8 matched unrelated donor will be include in these analyses.

We will separately summarize safety and other data for patients who receive pacritinib but who do not undergo stem cell transplant.

We will perform a descriptive statistical analysis of the Participant Follow-up Assessment questionnaire (Global Impression of Change Scale, Appendix F.) data collected at approximately 1, 3, 6, and 12 months post-transplant.

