7.0 Criteria for Removal from the Study

- 7.1 Any toxicity that is deemed unacceptable by the study PI.
- 7.2 Disease progression.
- 7.3 Lack of compliance with the requirements of the study.
- 7.4 Withdrawal of consent.
- 7.5 After one year of transplant.

7.6 No matched related or less than 7/8 matched unrelated donor.

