8.0 Adverse Events and Reporting Requirements

8.1 AEs during Pacritinib phase

The severity of the adverse events (AEs) will be graded according to the Common Terminology Criteria v4.0 (CTCAE). We will not capture expected Grade 1 and Grade 2 AEs. Grade 3 and 4 AEs will be collected and recorded in the medical record. Only Pacritinib-related adverse events and protocol specific data will be entered into PDMS/CORe. PDMS/CORE will be used as the electronic case report form for this protocol.

Events not included in the CTCAE chart will be scored as follows: General grading:

Grade 2: Moderate: discomfort present with some disruption of daily activity, require treatment.

Grade 3: Severe: discomfort that interrupts normal daily activity, not responding to first line treatment.

Grade 4: Life Threatening: discomfort that represents immediate risk of death

Causality Assessment

For the purpose of this study, events known to be caused by Pacritinib will be assessed as definitely related.

Events known to be caused by components of the transplant package and its direct consequences as well as those events known to be related to drugs used for the treatment of GVHD, infections and supportive treatment will be scored as unrelated.

When the relationship of the adverse event cannot be ruled out with certainty the AE may be considered possibly related.

The PI will be responsible for assessing the causality and will be final arbiter. Documentation of grade, onset/resolution date and attribution will be entered into the patient's medical record and signed by the PI.

Collection of adverse events

Collection of adverse events will reflect the onset and resolution date and maximum grade. Intermittent events should be labeled as such and followed until resolution. If a patient is taken off study while an event still ongoing, this will be followed until resolution unless another therapy is initiated. Pre-existing medical conditions will be recorded only if an exacerbation occurs during the active treatment period. Co-morbid events will not be scored separately.

Adverse events related to Pacritinib will be collected and recorded for the duration of active treatment plus 14 days.

List of expected adverse events related to Pacritinib: Occurring in >10% include:

1. Nausea, vomiting, diarrhea, dehydration

- 2. Anemia, thrombocytopenia
- 3. Fatique

Treatment Duration Definitions:

Active Treatment: patients receiving Pacritinib.

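### For a patient with no matched donor and no haploidentical transplant, 4.1.4 allows pacritinib to continue and 4.7 does not remove the patient, but Section 6 and 7.6 do; separately, haploidentical recipients fall outside both safety summaries

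*Combined protocol and SAP*

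**What the plan says.** In this point, a matched donor means a matched related donor or an unrelated donor matched at 7/8 or better.

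**Continuing drug and study status**
- Section 4.1.4, on patients who do not reach the standard-of-care transplant: "they will be able to continue treatment with Pacritinib until there is evidence of disease progression".
- Section 4.7, on patients without a suitable donor: those "who are going to undergo transplant from a haploidentical donor will come off study".
- Section 6.0, General, is wider: "Patients who do not have a suitable related or unrelated donor will come off study and may receive a transplant from a haploidentical donor".
- Section 7.6 lists this among the criteria for removal from the study: "No matched related or less than 7/8 matched unrelated donor".

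**Data collection**
- Section 5.2: "The monthly visits will continue as long as patient is taking Pacritinib". These visits include blood counts, chemistry and an EKG.
- Section 8.1: "Adverse events related to Pacritinib will be collected and recorded for the duration of active treatment plus 14 days". Active treatment is defined there only as receiving pacritinib.
- The SAE reporting text in Section 8.0 runs capture to 14 days past the final dose and names withdrawal of consent as the one exception. Treatment-related SAEs after that window must also be reported.
- Section 8.1 also says that an event still ongoing when a patient goes off study is followed to resolution, unless another therapy begins.

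**Safety analysis**
- Section 6.0, Secondary Analyses, restricts the main safety tabulation to matched-donor transplant recipients and adds: "We will separately summarize safety and other data for patients who receive pacritinib but who do not undergo stem cell transplant".

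**The concern.** Staff treating a patient who has no matched donor, and who is not having a haploidentical transplant, cannot follow all four rules on treatment and study status. If the patient stays on pacritinib under 4.1.4 and is also removed under 7.6, an investigational drug is being taken by someone whose study status is off study. The plan does not say which study procedures then still apply.

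That matters for two reasons. Section 9.4 names QTc prolongation as an observed risk and advises routine ECG monitoring, and the monthly EKG in 5.2 is a study procedure. Section 6 also promises a safety summary of untransplanted patients, which is complete only if their data keep coming in for as long as they take the drug.

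A second gap concerns reporting only. A patient who takes pacritinib and then has a haploidentical transplant has undergone a transplant, but not from a matched donor. Neither safety summary, as worded, includes that patient.

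**Working it through.** **1. The plan's own figure.** Section 6 gives 21 evaluable patients for 80% power, with a one-sided 5% exponential MLE test of 1-year PFS of 61% against 80%, 3 years of accrual and 1 further year of follow-up. Taking those inputs as stated, with uniform accrual:
- Hazards per year: −ln 0.61 = 0.4943 and −ln 0.80 = 0.2231.
- Event probabilities: 0.682 under the null and 0.417 under the alternative.
- Hazard-scale formula: n = (1.645 × 0.4943/√0.682 + 0.842 × 0.2231/√0.417)² / (0.4943 − 0.2231)² = 22.1, so 23.
- Simulated power at n = 21 (200,000 runs, log-hazard Wald test): 0.818.

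The figure of 21 is thus reproduced to within the choice of test variant. It counts only matched-donor transplant recipients, so nothing below changes it.

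**2. The rules side by side, by type of patient.**

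| Patient on pacritinib | 4.1.4 | 4.7 | Section 6 | 7.6 | Consistent? |
|---|---|---|---|---|---|
| No matched donor, no haploidentical transplant | may continue | not removed | removed | removed | No |
| No matched donor, haploidentical transplant | not continuing drug | removed | removed | removed | Yes |
| Matched donor, but transplant not pursued | may continue | silent | silent | silent | Yes |
| Matched-donor transplant | not applicable | not removed | evaluable | not removed | Yes |

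Only the first row is in conflict. It falls under 4.1.4 because that rule is not limited by reason: it applies whatever keeps the patient from transplant.

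**3. Does data collection survive removal?** The monthly visits, the AE window and the SAE window are all keyed to taking the drug, not to study status. That favours continued collection. Against it, no section says that these procedures apply after removal under 7.6. The only rule written for off-study patients covers events already ongoing, and it ends if another therapy starts. New events with onset after removal, while the patient is still on drug, are left to interpretation.

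**4. Coverage of the safety summaries.** Row 4 is in the main tabulation. Rows 1 and 3 are in the separate summary of untransplanted patients. Row 2 is in neither.

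**5. Size.** Maximum enrolment of 40 less 21 evaluable is 19, and 19/40 = 47.5%. Section 6 gives two reasons for the excess: no suitable donor, and patients deciding against transplant. It does not divide the 19 between them, nor the no-donor patients between rows 1 and 2. The number in row 1 is therefore anywhere from 0 to 19, and so is the number in row 2, with the two together at most 19.

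**The case against.** The strongest reply is that the passages can be read in harmony. The Section 6 sentence also mentions haploidentical transplant, so it may be meant for the same narrow group as 4.7. Patients with no transplant at all would then stay on drug under 4.1.4 until progression, which is removal criterion 7.2. The planned summary of untransplanted patients fits that reading. It may well be the intention, but the wording does not say it. Section 6 takes off study all patients without a suitable donor and makes the haploidentical transplant optional. Criterion 7.6 carries no haploidentical condition. Nor is off study defined as merely outside the primary analysis: 7.6 stands beside toxicity, progression and withdrawal of consent, and the primary set is already restricted separately in Section 6.

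A reader might infer that these patients' data will be lost or their toxicity left unmonitored. The documents do not support that. Sections 5.2 and 8 tie visits, AE and SAE collection to drug intake, and this part of the reply stands. What remains is an ambiguity about whether those procedures continue after removal.

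A reader might also take 47.5% as the share affected. It is a ceiling for all non-evaluable patients. It includes those who decline transplant, for whom the rules agree, and haploidentical recipients, who are not the patients continuing drug.

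On the second gap, the phrase about patients not undergoing transplant could be stretched to mean the protocol transplant. The text does not say so, and the haploidentical procedure is itself called a transplant in Section 6.

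**Conclusion.** The plan is wrong as written on two counts: an internal contradiction among 4.1.4, 4.7, Section 6 and 7.6, and an incomplete safety set. The contradiction is confined to patients with no matched donor who do not go to a haploidentical transplant. Their number is unknown, 0 to 19 of 40. For them, 4.1.4 sets no calendar limit on exposure, whereas 4.1.2 has transplant-bound patients proceed within 180 days. Progression and the toxicity rules in 4.3 and 7.1 still bound it. The documents give no expected duration, so one cannot say that these patients will have the longest exposure.

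The omission of haploidentical recipients from both summaries is a separate reporting gap. Their pacritinib-phase events still fall within the collection window in 8.1.

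The conclusion assumes that 7.6 means having neither a matched related donor nor an unrelated donor at 7/8 or better, as Section 6 implies, and that lacking a donor counts as a reason under 4.1.4. There is no effect on N = 21 or on the primary analysis, which excludes all these patients.

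**What to change.** 1. Reconcile 4.1.4, 4.7, Section 6 and 7.6 so that they give one study status for a patient on pacritinib without a matched donor, with and without a haploidentical transplant. Whether such patients may continue drug is for the clinical team to decide.
2. State that lacking a matched donor excludes a patient from the primary-endpoint set, and that the existing 5.2 visits continue for as long as pacritinib is taken, with AE and SAE collection continuing for that time plus 14 days.
3. In Section 6, Secondary Analyses, widen the separate safety summary to all patients who received pacritinib but did not have a transplant from a matched donor, showing untransplanted patients and haploidentical recipients as distinct groups.

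The cost is protocol wording, minor extra data handling and one more group in a table. The visits and collection windows already exist, and the sample size and primary analysis stay as they are.

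### Section 4.2 allows same-dose restart of pacritinib after any drug-related hold, which contradicts two lines of Table 3, does not match 4.4.4, and leaves prolonged grade 4 toxicity under the loosest text

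*Combined protocol and SAP*

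**What the plan says.** Section 4.2 (Treatment Interruption) opens by naming adverse events, hematology and serum chemistry, so its scope is not confined to one kind of toxicity. It then says "Pacritinib treatment may be withheld for up to 4 weeks due to drug-related toxicities", with longer holds possible by agreement with the medical monitor, and continues: "After treatment interruption, patients may resume the pacritinib treatment at the same dose level or at a reduced dose level". It does not refer to 4.3 or 4.4.

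Section 4.3 deals with nonhematologic toxicity: "Dose management for nonhematologic toxicities is summarized in Table 3". The relevant lines of Table 3 are:
- Grade 3: hold. If resolved within 7 days, the line reads "treatment may be resumed at the same level or the next lower dose, at the discretion of the investigator"; the sponsor is to be consulted first. If not resolved within 7 days, the toxicity "requires dose reduction to the next lower dose level".
- Grade 4: hold. If resolved within 7 days, the line reads "treatment may be resumed, but dose will be reduced by one dose level from the level at which the toxicity was observed". Where it occurs at 200 mg/day, the patient is discontinued.

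Section 4.3.6 adds "The lowest dose of pacritinib used in the study will be 200 mg/day", and that a patient whose toxicity persists despite reduction to that dose stops treatment.

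Section 4.4.4 deals with hematologic toxicity. It calls for interruption when the investigator judges that myelosuppression has worsened to a clinically significant degree for more than 7 days, or when infection or bleeding accompanies it. On restart it says: "Pacritinib may be restarted at a reduced dose once the toxicity has resolved to grade ≤ 2 or to the baseline grade", with any complications also resolved.

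**The concern.** A general paragraph offers same-dose restart after any drug-related hold. More specific text then removes that option in some cases, and no order of precedence is written. Two clinicians who both follow the protocol could restart the same patient at different doses.

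The sharper problem is nonhematologic grade 4 toxicity that lasts longer than 7 days. The rule that forces a reduction is tied to resolution within 7 days. Once that window has passed, the only express words on resumption are those of 4.2. A patient with the longer toxicity could then be re-exposed at the dose that caused it, with no clear protocol deviation.

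These events are foreseeable. The Background (Pacritinib) reports grade 3 QTc prolongation and grade 3 diarrhea among the dose-limiting toxicities. Section 9.4 relies on interruption or dose reduction as the protocol directs to manage gastrointestinal and cardiac risk.

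**Working it through.** The plan states no figure on this point to reproduce. The check sets 4.2 beside the specific text for each type of toxicity, grade, time to resolution and dose level.

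**Dose levels**
- Start (4.1.1): 200 mg twice daily = 400 mg/day.
- First reduction (4.3.1): 200 + 100 = 300 mg/day.
- Second reduction (4.3.2): 100 + 100 = 200 mg/day, the lowest dose under 4.3.6.

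The levels agree with one another: two steps of 100 mg.

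**Comparison with 4.2, which always allows the same or a reduced dose**

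| Case | Specific text | Result |
|---|---|---|
| 1. Nonhematologic grade 3, resolved within 7 days | Same level or next lower (Table 3) | Agree on dose |
| 2. Nonhematologic grade 3, not resolved within 7 days | Reduction required (Table 3) | Contradiction |
| 3. Nonhematologic grade 4 above 200 mg/day, resolved within 7 days | One-level reduction (Table 3) | Contradiction |
| 4. Nonhematologic grade 4 above 200 mg/day, not resolved within 7 days | Hold; nothing on what follows (Table 3) | Gap; only 4.2 expressly addresses resumption |
| 5. Nonhematologic grade 4 at 200 mg/day | Discontinue, whatever the duration (Table 3) | Answered by Table 3; not part of the gap |
| 6. Hematologic hold above 200 mg/day | Only a reduced dose is mentioned, worded as permission (4.4.4) | Mismatch |
| 7. Hematologic hold at 200 mg/day, event resolved | Only a reduced dose is mentioned, but no lower dose exists (4.4.4, 4.3.6) | Gap |

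**Cases 3 and 4 together.** Take two patients at 400 mg/day with nonhematologic grade 4 toxicity. If it resolves on day 7, Table 3 requires 300 mg/day on restart. If it resolves on day 10, that line no longer applies, and 4.2 read literally permits 400 mg/day. Other readings of case 4 are open: no restart at all, since permission to resume depends on resolution within 7 days, or a reduced dose by analogy with the grade 3 row. The text does not choose among them.

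**Case 7.** The second sentence of 4.3.6 requires discontinuation, but it stands under the nonhematologic heading and concerns toxicity that persists. It does not clearly reach a hematologic event that has resolved.

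**Dose at stake where same-dose and one-level-reduced restart compete**
- From 400 mg/day: 100 / 400 = 25%.
- From 300 mg/day: 100 / 300 = 33%.

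**The case against.** The best defence is that 4.2 is a general, permissive paragraph listing the options found across the protocol. The type-specific guidelines follow directly, and a clinician would ordinarily let the specific rule prevail. On that reading, a same-dose restart in case 2 or 3 would simply breach Table 3. This softens those two conflicts, but the precedence is nowhere written. It cannot settle case 4, where no specific restart rule exists, or case 7, where the specific rule points to a dose that is not available.

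Several stronger readings are tempting, and the documents do not support them:
- *Table 3 always demands a reduction.* It does not. For grade 3 resolved within 7 days it offers the same options as 4.2.
- *Prolonged grade 4 toxicity is covered by 4.2 alone.* Table 3's hold applies to all nonhematologic grade 4 toxicity, discontinuation applies at 200 mg/day, 4.4.4 deals with prolonged myelosuppression, and 7.1 allows removal for unacceptable toxicity. The gap is confined to restart after nonhematologic grade 4 above the lowest dose.
- *The grade 3 line beyond 7 days lets a reduced dose be given while the toxicity continues.* That row begins with a hold, and a hold of up to 4 weeks is compatible with a reduced dose on restart.
- *The number of patients affected can be estimated.* A reader might apply the 16% rate of grade 3 or higher anemia or thrombocytopenia in the Background to the ceiling of 40 patients. The trigger in 4.4.4 is not based on grade, and that rate says nothing about nonhematologic grade 4 events.

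It is also fair to say that the statistical consequences are limited. Section 6.0 plans no analysis by dose level, and the primary endpoint is counted from transplant.

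**Conclusion.** The point holds as an internal contradiction with two unfilled cases. Section 4.2 contradicts Table 3 in two nonhematologic situations and does not match 4.4.4 on hematologic restart. For nonhematologic grade 4 above 200 mg/day lasting beyond 7 days, the literal result is a more permissive rule for the longer toxicity. A resolved hematologic event at the lowest dose has no clear answer in 4.4.4.

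The size is one dose level per restart where the two options compete, 25% or 33% of the daily dose. How often this would arise cannot be estimated from the documents. The sample size and the primary test are unaffected. The matter is patient safety and whether a restart can be judged compliant.

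The conclusion assumes that no order of precedence is given elsewhere and that no further rule exists in 4.3. In the copy reviewed, the numbering runs from 4.3.4 to 4.3.6. If a 4.3.5 exists in the source, it should be read first.

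**What to change.** Reconcile 4.2, Table 3, 4.3.6 and 4.4.4 in one amendment that does the following:
- State which text governs restart after an interruption.
- Complete Table 3 for nonhematologic grade 4 that does not resolve within 7 days above 200 mg/day.
- Complete 4.4.4 for a resolved hematologic event when the patient is already at the lowest dose, and say whether 4.3.6 reaches hematologic toxicity.

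The same amendment can settle a small related difference: at 200 mg/day, Table 3 discontinues the patient from the study, while 4.3.6 discontinues treatment.

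The clinical team decides the rule in each case; none is proposed here. The cost is a short wording amendment, with no added visits, tests or patients.
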